3.3.4 Evaluation Criteria

The active treatment therapy regimen (which includes OLE therapy with The Volara® System) will be evaluated to determine the effect on the frequency of pulmonary exacerbation and/or change in other clinical endpoints during the active treatment (OLE therapy) period. Endpoints are described below:

3.3.4.1 Primary Endpoint(s):**• Frequency of exacerbations of pulmonary disease**

Exacerbations of pulmonary disease are defined as changes in respiratory status requiring intervention. Documentation of pneumonia or respiratory infection, change in chest x-ray, changes in requirement for respiratory support necessitating any of the interventions below will be considered an exacerbation of pulmonary disease:

- Hospitalization
- Emergency Department (ED) Visit

PROTOCOL TITLE**Evaluation of Oscillation and Lung Expansion (OLE) using The Volara® System for treatment of respiratory complications in patients with neuromuscular disease in the home setting****Final Protocol****Protocol Number:** CR-RR-2020-005**Date:** 11May2022

- Antibiotics (oral, intravenous, or nebulized)
- Unscheduled Outpatient Clinic Visit

3.3.4.2 Secondary Endpoint(s):**• Hospital Admissions**

Total number of Hospital Admissions will be determined for each study subject by review of the medical record for pre-treatment period and for the active treatment period. Total Hospital Admissions will be determined for each subject and for the study group (Mean \pm SD) for each study period.

• Hospital Length of Stay

Total Hospital Length of Stay will be determined for each study subject by calculating the number of days spent in the hospital for each admission, from time of admission to time of discharge. The sum of all hospital days for each subject will be calculated for the pre-treatment period and for the active treatment period. Total Hospital Days will be determined for each subject and for the study group (Mean \pm SD) for each study period.

• ICU Admissions

Total number of ICU Admissions will be determined for each study subject by review of the medical record during the pre-treatment period and for the active treatment period. Total ICU Admissions will be determined for each subject and for the study group (Mean \pm SD) for each study period.

• ICU Length of Stay

Total ICU Length of Stay will be determined for each study subject by calculating the number of days spent in the ICU for each admission, from time of admission to time of discharge. The sum of all ICU days for each subject will be calculated for the pre-treatment period and for the active treatment period. Total ICU Days will be determined for each subject and for the study group (Mean \pm SD) for each study period.

• Number of Outpatient Visits

PROTOCOL TITLE

Evaluation of Oscillation and Lung Expansion (OLE) using The Volara® System for treatment of respiratory complications in patients with neuromuscular disease in the home setting

Final Protocol

Protocol Number: CR-RR-2020-005

Date: 11May2022

Total number of Outpatient Visits will be determined for each study subject by review of the medical record and identifying all visits defined as 1) physician office visits, 2) urgent care visits or 3) emergency department (ED) visits for pulmonary complications that occur during the pre-treatment period and during the active treatment period. Total Outpatient Visits will be determined for each subject and for the study group (Mean \pm SD) for each study period.

● Number of Antibiotic Use Days

Total number of Antibiotic Use Days for pulmonary exacerbation will be determined for each study subject by review of the medical record and by calculating the number of days of antibiotic use for each episode, from time of initiation to time of discontinuation. Antibiotic use will be further categorized and individual totals provided for 1) oral, 2) intravenous, and 3) nebulized antibiotic use for pulmonary complications that occur during the pre-treatment period and during the active treatment period. Total antibiotic days and totals for sub-categories will be determined for each subject and for the study group (Mean \pm SD) for each study period.

● Pulmonary Function Testing: Spirometry Measures, Oxygen Saturation and Maximal Inspiratory Pressure

Subject Pulmonary Function will be assessed at baseline and monthly during the active treatment period. Virtual visits will be conducted by pulmonary function specialists, as described above. The following measures will be collected:

- Slow Vital Capacity (SVC)
- Peak Cough Flow
- Resting SpO₂
- Maximal Inspiratory Pressure (MIP)

Baseline measures will be compared to measures obtained during the active treatment period.

● Quality of Life (QOL) Assessment

The Severe Respiratory Insufficiency (SRI) questionnaire will be administered to all study subjects by the study staff at baseline (reflecting pre-treatment therapy regimen) and during one-month, three-month and six-month study visits. Results will be determined for each subject and for the study group for each time period and will then be compared to determine any differences in QOL scores between the pre-treatment and active treatment time periods.

PROTOCOL TITLE

Evaluation of Oscillation and Lung Expansion (OLE) using The Volara® System for treatment of respiratory complications in patients with neuromuscular disease in the home setting

Final Protocol

Protocol Number: CR-RR-2020-005

Date: 11May2022

• Adherence to OLE Treatment Regimen

Adherence to the OLE treatment regimen will be determined by downloading device therapy log data during the active treatment period. Total adherence to the OLE treatment regimen will be determined for each subject and for the study group (Mean \pm SD) for the active treatment period.

• Patient/Caregiver Satisfaction with Therapy

A satisfaction questionnaire will be administered to all study subjects/caregivers by the study staff at baseline (reflecting the patient's pre-treatment therapy regimen) and at each subsequent study visit to assess satisfaction with OLE therapy. Results will be determined for each subject and for the study group for each time period and will then be compared to determine any differences in satisfaction scores between the pre-treatment and active treatment time periods.

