3.3.4 Study Exit Documentation

Study exit data is collected to document the reason participation in the study ended. Reasons for exit from the study include:

- **Completion of the study**
- **Subject inability to tolerate therapy**
- **Subject withdrawal**
This may be voluntary withdrawal on the part of the subject or subject caregiver or withdrawal by investigator for subjects deemed unfit for or unsafe to continue the trial
- **Subject death**

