3.3.5 Study Observations/Procedures Table

The study observations and documentation timeline are outlined in Table 1.

PROTOCOL TITLE

Evaluation of Oscillation and Lung Expansion (OLE) using The Volara® System for treatment of respiratory complications in patients with neuromuscular disease in the home setting

Final Protocol

Protocol Number: CR-RR-2020-005

Date: 11May2022

TABLE 1

Study Observations/Procedures

| Procedures | Baseline | Run-in | 1 month | 3 months | 6 months |
|---|------------------------------------|--------|---------|----------|------------------------------|
| Inclusion/Exclusion Criteria | X | | | | |
| Pregnancy test (women of childbearing age) | X | | | | |
| Informed consent (and assent if minor subject) | X ¹ | | | | |
| Demographics | X | | | | |
| Medical History | X | | | | |
| Baseline Pulmonary Medications | X | | | | |
| Documentation of acute pulmonary exacerbations: 
 Hospital admission and discharge (including ICU admission and discharge) Antibiotic use (IV/Oral/inhaled) start and stop dates Outpatient Visits for Pulmonary Complication 
 Physician Office Visits Urgent Care Visits ED Visits Documented from the medical record | X Retrospective (past 12 mo) | | | | X Active Treatment Period |
| QOL Questionnaire | X | | X | X | X |
| Patient/Caregiver satisfaction with Therapy | X | | X | X | X |
| Basic Pulmonary Function Measures 
 SVC PCF Resting SpO₂ Maximal Inspiratory Pressure (MIP) | X | | | | Monthly |
| Adherence to prescribed regimen (OLE) | | | | | Ongoing |
| Documentation of use of MIE or other airway clearance/lung expansion therapy/maneuvers | | X | | | |
| Adverse device effects | | | | | Each Occurrence |
| Study Exit Form | | | | | X |

PROTOCOL TITLE

Evaluation of Oscillation and Lung Expansion (OLE) using The Volara® System for treatment of respiratory complications in patients with neuromuscular disease in the home setting

Final Protocol

Protocol Number: CR-RR-2020-005

[figure not shown]
Date: 11 May 2022

¹Obtained prior to any study-specific procedures

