## 2.6 Other general principles

### 2.6.1 Handling of Dropouts or Missing data

All data collected up to the point where the patient drops out will be used for analyses. Missing data will not be imputed.

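### Cheap improvement: no quality-of-life or satisfaction form is planned at early exit, so the month-3 and month-6 summaries describe only subjects still in the study

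*Protocol*

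**What the plan says.** Protocol 3.3.4.2 gives the SRI "at baseline (reflecting pre-treatment therapy regimen) and during one-month, three-month and six-month study visits". The satisfaction questionnaire is given at baseline, where it rates the earlier regimen, and "at each subsequent study visit to assess satisfaction with OLE therapy". Table 1 marks both forms at baseline and months 1, 3 and 6, and has no early-exit column. Its Study Exit Form row is marked only under 6 months.

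Protocol 3.3.4 (Study Exit Documentation) states the purpose of the exit record: "Study exit data is collected to document the reason participation in the study ended". Among the listed reasons are "Subject inability to tolerate therapy" and withdrawal by the subject, caregiver or investigator. The synopsis allows removal for intolerance, or for inability or unwillingness to perform the therapy. Section 3.2.2 treats inability or unwillingness as a reason to exit a subject.

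In the SAP, section 2.1.4 has data recorded up to discontinuation, and section 2.6.1 uses those data but adds: "Missing data will not be imputed". Sections 2.4.2.8.2 and 2.4.2.9.2 summarise quality of life and satisfaction visit by visit in the FAS. Section 2.1.3 keeps results from unscheduled visits out of the summary tables and shows them only in listings.

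**The concern.** Both outcomes are secondary endpoints, and protocol 3.3.4.2 sets the pre-treatment scores against the on-treatment scores. Every treated subject should have a baseline form, but only subjects still in the study have a month-6 form. Someone who leaves because the therapy is intolerable or unwanted is likely to rate it lower than someone who stays, so absence is related to the answer. In a single-arm, open-label study, no comparison group shows how much of a favourable month-6 figure comes from selection.

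Two features of the SAP raise the stakes. Section 3 drops the adherence analysis, so satisfaction carries more of the weight as evidence of acceptability. And if a site gave the forms at exit on its own initiative, section 2.1.3 could leave the results out of the tables. The assessment helps only if it is planned.

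**Working it through.** The plan has no figure of its own to reproduce: the sample of about 70 is a convenience sample and no dropout rate is given. The check has two parts. All dropout and satisfaction values below are assumptions, and 70 subjects are taken to start therapy.

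**1. Who lacks a rating.** Let d be the proportion leaving by month 6. With a constant exit rate, h = -ln(1-d)/6 per month and S(t) = exp(-ht). Expected exits between t1 and t2 are 70 × [S(t1) - S(t2)]. For example, d = 0.20 gives h = 0.0372 and S(1) = 0.963, so exits before month 1 are 70 × (1 - 0.963) ≈ 2.6.

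| d | Exits | Before month 1 | Months 1-3 | Months 3-6 | Exits with at least one on-therapy form | In study at months 1 / 3 / 6 |
|---|---|---|---|---|---|---|
| 10% | 7 | 1.2 | 2.4 | 3.4 | 83% | 69 / 66 / 63 |
| 20% | 14 | 2.6 | 4.8 | 6.6 | 82% | 67 / 63 / 56 |
| 30% | 21 | 4.0 | 7.4 | 9.6 | 81% | 66 / 59 / 49 |

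If instead half of all exits came before month 1, then 3.5, 7 or 10.5 subjects would have no on-therapy rating, and at most 50% of leavers would have one.

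**2. Effect on the month-6 satisfaction figure.** Let p_c be the proportion of completers giving a favourable answer and p_s the proportion among those who stop. The table shows p_c. The all-treated figure is (1-d)p_c + d·p_s, so the gap is d(p_c - p_s).

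With p_c = 85%, the gap in percentage points is:

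| d | p_s = 20% | p_s = 40% | p_s = 60% |
|---|---|---|---|
| 10% | 6.5 | 4.5 | 2.5 |
| 20% | 13.0 | 9.0 | 5.0 |
| 30% | 19.5 | 13.5 | 7.5 |

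With p_c = 80% and p_s = 20%, the all-treated figure is 74%, 68% or 62%, a gap of 6, 12 or 18 points. The mildest corner of the range is p_c = 80%, p_s = 60%, d = 10%: 0.10 × (80 - 60) = 2 points. Over the whole range the gap is 2 to 19.5 points.

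**Quality of life.** The same identity holds for mean change from baseline: the completers' mean exceeds the all-treated mean by d times the difference between completers and stoppers. The documents contain nothing that fixes the sign or size of that difference, so no figure is claimed.

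**The case against.** A reader might infer that the views of those who fail on the device are never recorded. The documents do not support that. Only subjects who stop before month 1 have no on-therapy rating. Later leavers have a month-1 or month-3 form, and SAP 2.1.4 and 2.6.1 record and use it; under a constant exit rate that covers just over 80% of leavers. Baseline forms exist for them too.

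Failure of the device also shows elsewhere. The protocol records exit reasons, records adverse device effects at each occurrence, and counts complaints. SAP 2.2 tabulates withdrawals by reason, and Table 14.3.1.1.6 covers adverse events leading to discontinuation. This stands, but none of it is a satisfaction or SRI score. The discontinuation reasons named in SAP 2.1.4 also do not include intolerance, so such exits could fall under another category.

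It is an inference that the exit form holds nothing beyond the reason: the form is not in the documents, and the protocol states only its purpose. Nor need stopping the device mean leaving the study, because the synopsis says removal may occur. A subject who stops but stays would still meet scheduled visits.

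It is also tempting to say that the quality-of-life result is biased in the device's favour. That is not shown: the analysis includes change from baseline, so a difference in leavers' starting level does not by itself bias it. For satisfaction, exits include deaths and losses to follow-up, so very low satisfaction should not be assigned to every leaver. SAP 2.4.2.9.2 plans results by question, so the percentages above stand for the favourable share on one question.

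Finally, this is a descriptive pilot without hypothesis tests. That limits the weight of the point, but the percentages will still be reported and read.

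**Conclusion.** The point holds as a cheap improvement to secondary endpoints; it does not identify an error or contradiction. No form is planned at early exit, early stoppers give no on-therapy rating, later stoppers give none at stopping, and the unimputed month-3 and month-6 summaries describe those who remained. For satisfaction the selection probably favours the device, by about 2 to 20 percentage points at month 6 if 10-30% leave, 80-85% of completers are satisfied and 20-60% of stoppers are. These inputs are assumed, so the range illustrates sensitivity and is not an estimate. The gap is positive whenever leavers are less satisfied than stayers. The direction for quality of life remains open.

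**What to change.** **Protocol 3.3.4 (Study Exit Documentation) and Table 1.** Add the satisfaction survey and the SRI at early exit, by phone or virtually, for subjects who agree. Define this as a planned exit assessment so that SAP 2.1.3 does not remove it from the tables.

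**SAP Tables 14.2.4.1 and 14.2.5.2.** Show the number contributing and the number missing at each visit. Add the last available on-therapy rating for all treated subjects in the FAS, split by completed or discontinued. Label exit-form values separately from on-device values, since a form completed after stopping is not an on-device score.

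**If data collection has ended.** SAP version 2.0 is dated 28 May 2024 and section 2.6.2 speaks of the study in the past tense, so this is possible. In that case make only the table changes and state the missing exit ratings as a limitation.

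**Cost.** A short amendment and one brief contact per early leaver, with existing staff and forms. Some leavers will decline, perhaps the least satisfied, so the gap narrows but may not close. The last-rating row mixes time points and should be read as a supplement to the visit tables. The satisfaction figure may look less favourable.

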3.3.4 Study Exit Documentation

Study exit data is collected to document the reason participation in the study ended. Reasons for exit from the study include:

- **Completion of the study**
- **Subject inability to tolerate therapy**
- **Subject withdrawal**
This may be voluntary withdrawal on the part of the subject or subject caregiver or withdrawal by investigator for subjects deemed unfit for or unsafe to continue the trial
- **Subject death**

3.3.5 Study Observations/Procedures Table

The study observations and documentation timeline are outlined in Table 1.

PROTOCOL TITLE

Evaluation of Oscillation and Lung Expansion (OLE) using The Volara® System for treatment of respiratory complications in patients with neuromuscular disease in the home setting

Final Protocol

Protocol Number: CR-RR-2020-005

Date: 11May2022

TABLE 1

Study Observations/Procedures

| Procedures | Baseline | Run-in | 1 month | 3 months | 6 months |
|---|------------------------------------|--------|---------|----------|------------------------------|
| Inclusion/Exclusion Criteria | X | | | | |
| Pregnancy test (women of childbearing age) | X | | | | |
| Informed consent (and assent if minor subject) | X ¹ | | | | |
| Demographics | X | | | | |
| Medical History | X | | | | |
| Baseline Pulmonary Medications | X | | | | |
| Documentation of acute pulmonary exacerbations: 
 Hospital admission and discharge (including ICU admission and discharge) Antibiotic use (IV/Oral/inhaled) start and stop dates Outpatient Visits for Pulmonary Complication 
 Physician Office Visits Urgent Care Visits ED Visits Documented from the medical record | X Retrospective (past 12 mo) | | | | X Active Treatment Period |
| QOL Questionnaire | X | | X | X | X |
| Patient/Caregiver satisfaction with Therapy | X | | X | X | X |
| Basic Pulmonary Function Measures 
 SVC PCF Resting SpO₂ Maximal Inspiratory Pressure (MIP) | X | | | | Monthly |
| Adherence to prescribed regimen (OLE) | | | | | Ongoing |
| Documentation of use of MIE or other airway clearance/lung expansion therapy/maneuvers | | X | | | |
| Adverse device effects | | | | | Each Occurrence |
| Study Exit Form | | | | | X |

PROTOCOL TITLE

Evaluation of Oscillation and Lung Expansion (OLE) using The Volara® System for treatment of respiratory complications in patients with neuromuscular disease in the home setting

Final Protocol

Protocol Number: CR-RR-2020-005

[figure not shown]
Date: 11 May 2022

¹Obtained prior to any study-specific procedures

3.3.6 Study Flow and Timeline

The study flow and timeline of events and data collection periods is shown below in and Figure 1.

FIGURE 1

PROTOCOL TITLE**Evaluation of Oscillation and Lung Expansion (OLE) using The Volara® System for treatment of respiratory complications in patients with neuromuscular disease in the home setting**

Final Protocol

Protocol Number: CR-RR-2020-005**Date:** 11May2022**3.5 Statistical Methods and Analysis****3.5.1 Sample Size Estimation**

The sample size for this study is a convenience sample. Resulting data on the outcomes associated with the OLE may provide preliminary data on effectiveness of therapy and help to provide definition of the effect size and variability and the number of subjects required for subsequent studies.

3.5.2 Statistical Analysis

- Summary statistics and data listings will be provided.
- Demographic data will be summarized. For continuous type data (e. g. Age), descriptive summary statistics (N, mean, median, standard deviation, min, and max) will be presented. For categorical variables (gender, race, etc.) the number and percent of subjects in each category will be provided.
- Endpoints will be documented and compared as described below:

Primary Endpoints:

Frequency of Exacerbation of Pulmonary Disease (as defined in section 3.3.4.1) along with 95% confidence interval will be generated. A detailed description of the analysis plan along with specific subsets to be summarized will be described in a separate document (the statistical analysis plan).

Secondary Endpoints:

The secondary endpoints (listed in section 3.3.4.2) will be summarized with descriptive summary statistics appropriate for continuous or categorical data, depending on the outcome being summarized:

1. Hospital Admissions
2. Hospital LOS
3. ICU Admissions

PROTOCOL TITLE**Evaluation of Oscillation and Lung Expansion (OLE) using The Volara® System for treatment of respiratory complications in patients with neuromuscular disease in the home setting****Final Protocol****Protocol Number:** CR-RR-2020-005**Date:** 11May2022

4. ICU LOS
5. Number of Outpatient Visits
6. Antibiotic Use Days
7. Pulmonary Function Testing
 - SVC
 - PCF
 - Resting SpO₂
 - MIP
8. QOL Assessment
9. Adherence to OLE Therapy Regimen
10. Patient/Caregiver Satisfaction

Comparison of Pre-treatment and Active Treatment Periods

Rate of exacerbation and health care utilization will be evaluated to compare the active treatment period and the control periods (six-month period immediately prior to active treatment and six-month seasonally equivalent time-period). Remaining endpoints will compare baseline assessments to assessments obtained during the active treatment period. Comparisons will be conducted for the purpose of identifying any statistical associations that can be attributed to use of OLE treatment with The Volara® System.

General Study Information**4.1 Technical Support for Device(s)**

Technical support will be performed by Hillrom following routine service practices (contact details will be provided).

4.2 Record Retention

PROTOCOL TITLE**Evaluation of Oscillation and Lung Expansion (OLE) using The Volara® System for treatment of respiratory complications in patients with neuromuscular disease in the home setting**

Final Protocol

Protocol Number: CR-RR-2020-005**Date:** 11May2022

Records must be maintained for a period of up to three years after the latter of the following dates: the date the study is completed/terminated, or the date of the last regulatory approval. The Investigators or Institutions shall notify the Sponsor at least thirty (30) days prior to any planned destruction of records from this study.

All records will be kept confidential and the patient's name will not be released at any time. Code numbers will be used to de-identify patient information on the CRFs and other study-related documents.

5.0 Safety and Device Complaint Definitions and Reporting Requirements

Safety surveillance within this study and the safety reporting both performed by the investigator, starts as soon as the subject signs informed consent (and assent if minor subject) and receives the first study-specific treatment. The safety surveillance and the safety reporting will continue until the last study-specific test has been performed, the subject/investigator concludes his participation into the study or the subject/investigator withdraws the subject from the study, except as otherwise specified in the protocol.

Reportable events:

- (1) Adverse Device Effects (adverse event related to the device) associated with the use of The Volara® System
- (2) Device Complaints associated with The Volara® System

During the study, safety events and device complaints must be reported to the Sponsor within 24 hours of becoming aware of the event. Please contact [REDACTED] by phone: [REDACTED] or email: [REDACTED].

PROTOCOL TITLE

Evaluation of Oscillation and Lung Expansion (OLE) using The Volara® System for treatment of respiratory complications in patients with neuromuscular disease in the home setting

Final Protocol

Protocol Number: CR-RR-2020-005

Date: 11May2022

A complaint is defined as any written, electronic or oral communication that alleges deficiencies related to the identity, quality, durability, reliability, safety, effectiveness, or performance of the device after its release for distribution (21 CFR 820.3(b)).

Any device Complaint and/or reported safety event be reviewed, evaluated, and investigated by Hillrom and reported to the appropriate Health Authority per current regulations.

Additional information may be requested, when required, by the Sponsor in order to support the reporting of safety events to regulatory authorities.

The investigator must notify the IRB/EC, if appropriate, in accordance with national and local laws and regulations, of the safety and/or complaint events reported to the Sponsor.

